 - Note: All trough samples should be drawn within 24 hours before infusion of pembrolizumab. Peak sample should be drawn within 30 minutes after the end of the infusion.

Approved

- Tumor response will be assessed using modified irRC-RECIST ([Appendix F](#)), at day 1 of week 12 (+1 week) and every 12 weeks (+1 week) thereafter or more frequently if clinically indicated until confirmed iPD or start of new anticancer treatment. Response (iCR, or iPR) or iPD to be confirmed by second consecutive response assessment no less than 4 weeks from the date of the first documented response or iPD. Subjects who have reached a confirmed iCR may increase their interval of radiographic assessments up to 6 months after the first 2 years beyond confirmed iCR and up to 12 months after the first 5 years beyond confirmed iCR as long as iCR is maintained.
 - Radiographic tumor imaging assessments must include CT scan, PET/CT, or MRI of the abdomen, pelvis, and chest and all other sites of disease. In addition, CT scan or MRI of the brain will only be performed if signs or symptoms suggestive of CNS metastasis are present. Imaging will be performed independent of treatment cycle at day 1 of week 0 (phase 1b only), day 1 of week 12 (+1 week), and then every 12 weeks (+1 week) or more frequently if clinically indicated until confirmed iPD per modified irRC-RECIST ([Appendix F](#)), or start of new anticancer treatment. Imaging should not be adjusted for cycle initiation delays and performed according to the calendar. The imaging modality selected (eg, CT or MRI) should remain constant for any individual subject.
 - Photographs of visible cutaneous and subcutaneous:
 - Photographs of all visible (ie, visible protrusion from skin surface) cutaneous and subcutaneous tumor lesions not detectable on radiographic imaging must be performed at screening within 28 days prior to enrollment for the purposes of documentation of baseline lesion data. It is critical that baseline photography is captured for subjects with visible cutaneous and subcutaneous tumor lesions in order to allow for follow up of these lesions during the treatment phase.

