10.5.4.1 PFS and iPFS Sensitivity Analyses

The following set of analyses will be used to assess the robustness of the PFS and iPFS primary analysis given the potential for ascertainment or time bias due to skipped or unscheduled tumor assessments, or deaths in the absence of prior radiologic evidence of progression that are remote from the last evaluable tumor assessment, and also to assess the impact of subsequent anti-cancer therapy.

- Stratified log-rank and Cox model analyses will be repeated in which PFS/iPFS times not associated with death in the absence of PD/iPD, that are outside of a + 1 week scheduled assessment window, are moved to the next scheduled post-randomization assessment day on both treatment arms. Times will not be moved if the next scheduled assessment is beyond the date of death or the analysis data cutoff date. This analysis will also be performed moving the same PFS/iPFS times to the closest assessment day.
- Stratified log-rank and Cox model analyses will be repeated in which PFS/iPFS death events that occur more than 13 weeks (12 weeks + 1 week window) after the last evaluable radiologic tumor assessment will be censored at the time of the last evaluable radiologic tumor assessment ([Dodd, 2008](#)).
- A complementary log-log model ([Allison, 1997](#)) will be used to estimate the hazard ratio of talimogene laherparepvec in combination with pembrolizumab compared to pembrolizumab alone adjusting for the randomization stratification factors as well as PD-L1 status at baseline (positive vs not positive). The complementary log-log model is based on a Cox model for continuous time in that the data will be grouped into time intervals. Twelve-week time intervals will be used to match the tumor assessment schedule.
- The impact of subsequent anti-cancer therapy on PFS/iPFS will be assessed by summarizing the incidence by treatment arm of selected anti-cancer therapies with potential PFS/iPFS benefit, the timing of such therapies among subjects that received it, and treatment HR estimates of time to first use among all subjects. Stratified log-rank and Cox model analyses will be repeated in which PFS/iPFS censoring at the last evaluable tumor assessment prior to the start of the first selected anti-cancer therapy.

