In the event of inadvertent Suspected Unexpected Serious Adverse Reaction (SUSAR) unblinding, an additional sensitivity analysis for PFS will be performed to assess the potential effect of the unblinding, by removing all event data after the date of the SUSAR unblinding from the analysis.

For the iPFS endpoint, analyses will be repeated if applicable imputing an event at the time of a last overall visit response of iPD that was not confirmed as required per modified irRC-RECIST.

Additionally, to assess the robustness of the PFS and iPFS primary and supportive analyses given the potential for bias related to potential informative censoring, the analyses noted for OS potential censoring in [Section 10.5.4.2](#) will be repeated for PFS and iPFS. Censoring times will be classified as (1) administrative (random) if within 91 days (corresponding to maximum lag time allowable between tumor assessments) of the analysis data cutoff date or otherwise (2) informative.

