10.5.4.2 OS Sensitivity Analyses

The following set of analyses will be used to assess the robustness of the OS primary analysis given the potential for bias related to informative censoring, and also to assess the impact of subsequent anti-cancer therapy.

- OS potential informative censoring will be assessed with a competing risks analysis utilizing the Fine-Gray proportional subdistribution hazards model ([Fine, 1999](#); [Gray, 1988](#)) (see code fragment in [Appendix C](#)). Censoring times will be classified as (1) administrative (random) if within 140 days (corresponding to maximum lag time allowable between long term follow up assessments) of the analysis data cutoff date or otherwise (2) informative. Type (2) censoring will be defined as a competing risk event. Gray's test will be performed and the Fine-Gray treatment HR with 95% CI will be calculated stratified as per dual primary efficacy endpoints.
- The impact of subsequent anti-cancer therapy on OS will be assessed by summarizing the incidence by treatment arm of selected anti-cancer therapies with potential OS benefit, the timing of such therapies among subjects that received it, and K-M and treatment HR estimates of time to first use among all subjects. OS analyses will be repeated in which OS is censored at the first selected anti-cancer therapy.
- Since this analysis may introduce bias due to dependent censoring, the OS effect will also be estimated with an inverse probability censoring weighting (IPCW) method (see code fragment in [Appendix C](#)) that incorporates a pre-specified covariate history (eg, grouped stage of disease (not IVRS), LDH, SLD, change in ECOG performance score, *BRAF* mutation (not IVRS), PD-L1, **and** time to progression per irRC-RECIST.) and outcomes up to the start of subsequent anti-cancer therapy ([Robins et al., 2000](#))

In the event of inadvertent SUSAR unblinding, an additional sensitivity analysis for OS will be performed to assess the potential effect of the unblinding, by removing all event data after the date of the SUSAR unblinding from the analysis.

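### The check for informative censoring codes loss to follow-up as a Fine-Gray competing event, so it shows one best-case scenario and cannot respond to what happens to subjects after they are lost

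*SAP*

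**What the plan says.** SAP 10.5.4.2 opens its OS sensitivity analyses with potential informative censoring, to be assessed by "a competing risks analysis utilizing the Fine-Gray proportional subdistribution hazards model", together with Gray's test. A censoring time is "administrative (random) if within 140 days" of the data cutoff and otherwise informative, called type (2). The instruction for the second group is: "Type (2) censoring will be defined as a competing risk event". The code in SAP Appendix C.8 agrees: status 2 is the competing risk and the event of interest is code 1.

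SAP 10.5.4.1 carries "the analyses noted for OS potential censoring in" 10.5.4.2 over to PFS and iPFS, where a censoring time is "administrative (random) if within 91 days (corresponding to maximum lag time allowable between tumor assessments". Another PFS/iPFS sensitivity analysis in that section censors "PFS/iPFS death events that occur more than 13 weeks (12 weeks + 1 week window) after the last evaluable radiologic tumor assessment".

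On imaging, Protocol 7.2.2 states that phase 3 subjects with a confirmed iCR "may increase their interval of radiographic assessments up to 6 months after the first 2 years beyond confirmed iCR".

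SAP 10.5.4 makes every p-value from the sensitivity analyses descriptive. Protocol 10.2.2 plans a single loss rate for both arms: 5% per year for OS and 10% for PFS.

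**The concern.** A competing risk is an event after which the event of interest cannot occur. A subject lost to follow-up can still die; Protocol 12.4 even has investigators search public records for survival status after withdrawal. Fine-Gray nevertheless leaves a type (2) subject in the risk set after loss and never records a death for that subject. Two consequences follow.

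- Nothing after loss enters the estimate, so it is the same whether lost subjects do well or badly.
- The subdistribution hazard falls in an arm simply because that arm loses subjects faster, whether or not the loss is related to prognosis.

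The usual fear about informative loss is that lost subjects, perhaps more in one arm, do worse than those who stay. This analysis assumes the opposite in both arms, so it does not stress the primary result. No other planned analysis varies the outcome of subjects lost from OS. The inverse-probability weighting in SAP 10.5.4.2 concerns subsequent anticancer therapy. Clark's completeness index and the follow-up plots (SAP 10.5.1.1) and the disposition tables (SAP 10.2) only describe follow-up. The one event imputation, in SAP 10.5.4.1, is for an unconfirmed last iPD in iPFS.

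**Working it through.** **Inputs from Protocol 10.2.2.** 660 subjects, 1:1; OS HR 0.70; control median OS 28 months, with 0.31 at month 48 and 0.27 at month 60; 26-month enrollment, half of it accrued by two thirds of the period; loss 5% per year. The OS primary analysis is put at month 75 (Protocol Tables 9 and 12). **Assumptions not in the documents:** loss rates that differ by arm, and a multiplier k on the death hazard after loss.

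**1. The plan's own figures reproduce.** Schoenfeld events are 4(z₁+z₂)²/(ln HR)².
- OS: 4 × (2.005+1.282)²/(ln 0.70)² = 4 × 10.80/0.1272 = 340. Freedman's formula gives (1.70/0.30)² × 10.80 = 347. The plan says 346.
- PFS, HR 2/3 at 0.005: 4 × 16.72/0.1644 = 407, as planned.
- The SAP Appendix B spending function gives nominal levels 0.0150, 0.0187, 0.0261 and 0.0336, and about 90% power, as tabulated.

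**2. Hand check of the mechanism.** With constant death hazard h and loss hazard r, the cumulative incidence of observed death is F(t) = h/(h+r) × (1−exp(−(h+r)t)). Take h = ln 2/28 = 0.02476 per month in both arms (no effect), r = −ln(0.90)/12 = 0.00878 in arm 1 and −ln(0.95)/12 = 0.00427 in arm 2.
- Month 28: F = 0.450 and 0.474; ratio of −ln(1−F) = 0.597/0.643 = 0.93.
- Month 60: F = 0.639 and 0.703; ratio = 1.020/1.215 = 0.84.

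The two arms have identical survival, yet the subdistribution comparison favours the arm with the higher loss rate.

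**3. Simulation on the protocol's OS curve** (600,000 subjects, unstratified, month 75, 140-day rule). Full data means that deaths after loss are known.

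| On-study HR | Loss per year, arm 1/arm 2 | Hazard after loss | Full data | Cox | Fine-Gray |
|---|---|---|---|---|---|
| 0.70 | 5%/5% | unchanged | 0.698 | 0.698 | 0.709 |
| 0.70 | 7.5%/5% | unchanged | 0.698 | 0.697 | 0.667 |
| 0.70 | 10%/5% | unchanged | 0.701 | 0.702 | 0.635 |
| 0.70 | 5%/10% | unchanged | 0.702 | 0.702 | 0.809 |
| 1.0 | 5%/5% | unchanged | 0.998 | 0.999 | 1.000 |
| 1.0 | 10%/5% | unchanged | 1.003 | 1.003 | 0.890 |
| 1.0 | 5%/10% | unchanged | 0.997 | 0.998 | 1.127 |
| 0.70 | 5%/5% | ×3, arm 1 | 0.775 | 0.695 | 0.708 |
| 0.70 | 10%/5% | ×3, arm 1 | 0.860 | 0.704 | 0.635 |
| 1.0 | 10%/5% | ×3, arm 1 | 1.187 | 1.000 | 0.888 |

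In the last two rows Fine-Gray moves away from the full-data value.

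**4. Insensitivity.** On-study HR 0.80, loss 10%/5%, same random seed, k applied in both arms:

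| k | 0 | 0.3 | 1 | 3 | 10 |
|---|---|---|---|---|---|
| Full data | 0.718 | 0.747 | 0.800 | 0.883 | 0.954 |
| Fine-Gray | 0.7175 | 0.7175 | 0.7175 | 0.7175 | 0.7175 |

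Fine-Gray equals the full-data value only at k = 0, when no lost subject dies before cutoff.

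**5. Trials of 660, true HR 1.0, harmless 10%/5% loss (2,000 runs).** Apparent one-sided significance for the combination occurs in 24.1% of Fine-Gray runs against 2.0% of Cox runs at month 75 (z < −1.96). The design curve gives 347 deaths at month 57.5 and 398 at month 75; Table 9 also uses external projections, so this is not an error. At month 57.5 the rates are 13.6% and 2.2% (z < −2.005), and the Fine-Gray HR is 0.907.

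**6. Subjects affected.** At the planned 5% per year, about 45 + 39 = 84 of 660 are type (2) at month 75, and 35 + 32 = 67 at month 57.5.

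**7. PFS at month 48.** Harmless loss of 20%/10% gives Fine-Gray 0.626 for a true 0.667 and 0.933 for a true 1.0. At the planned 10%/10% it gives 0.669 and 0.997.

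**8. Scan interval.** The 91 days are 84 + 7. A subject more than 2 years past confirmed iCR may be scanned at up to 6 months and so pass 91 days, or 13 weeks, with no scan missed. Suppose CR in 20% and 6% (Protocol 10.2.2) and, as assumptions, 5–10% relapse per year with every eligible responder using the long interval. Then about 9–11 arm 1 and 3 arm 2 subjects are mislabelled at month 48. Mislabelling 11 and 3 moves the Fine-Gray HR from 0.670 to 0.669 (true 0.667) and from 1.008 to 1.006 (true 1.0).

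**The case against.** The strongest reply has four parts.

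- **Nothing confirmatory depends on these analyses.** This stands. The rates in step 5 are not error rates of any trial decision. A reader might infer that the primary OS result or its type I error is compromised; SAP 10.5.4 rules that out.
- **The shift needs loss rates that differ by arm, in a double-blind trial planned with one rate.** This stands. Survival contact every 12 weeks (Protocol 7.2.4) and public-record searches (Protocol 8.1 and 12.4) should also limit loss. A reader might infer that the documents predict unequal loss; they do not. Equal rates remove most of the shift but not the insensitivity.
- **No analysis of observed data can detect informative loss.** This also stands. The complaint is therefore not that another method would detect it, but that the check explores a single assumption, and the favourable one. A tipping-point analysis displays a range of assumptions.
- **Fine-Gray is a valid bound.** It is one definable scenario, with lost subjects surviving to cutoff. The SAP does not present it as that.

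Two further overstatements are tempting. Lost subjects are not assumed immortal: the assumption covers type (2) loss only and ends at cutoff. Nor does the HR follow the number lost: at 5%/5% and HR 0.70, arm 1 has more lost subjects (45 against 39 per 330), yet the HR moves slightly towards the null. The direction follows the loss rate.

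**Conclusion.** The concern holds as a limitation of a descriptive sensitivity analysis. Coding type (2) loss as a competing event yields one best-case scenario for both arms, and the estimate cannot vary with prognosis after loss. That follows from the model and needs no simulation. The false shift is conditional. It takes the Fine-Gray HR to about 0.89 for a true 1.0 under an assumed 10% against 5% per year, and it is about 0.01 at the planned equal 5%. The harm is a misleading statement about robustness in either direction; the primary analyses stand.

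The scan-interval conflict is real but minor. A reader might infer that it could distort PFS materially, or that the protocol's 12-month interval, allowed beyond 5 years in confirmed iCR, adds to it. Neither is supported. The estimated change in the PFS HR is 0.001 to 0.002, and nobody can be 5 years past iCR at the planned month-48 PFS cutoff (SAP Table 4 prints month 44).

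**What to change.** In SAP 10.5.4.2, and by reference in 10.5.4.1, make the informative-censoring check a delta-adjusted multiple imputation. For each type (2) subject, impute residual time from the same arm and stratum with the hazard multiplied by 1, 1.5, 2 and 3, first in arm 1 only and then in both arms. Report the HR at each delta and the delta at which the conclusion changes. If Fine-Gray is kept, label it as the scenario in which lost subjects survive to cutoff.

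The replacement behaves as intended in the 10%/5% setting at month 75. With harmless loss, delta 1 gives 0.704 (full data 0.704) and 0.999 (1.000). With tripled hazard in lost arm 1 subjects, delta 3 gives 0.860 (0.859), 0.972 (0.973) and 1.190 (1.188) for on-study HRs of 0.70, 0.80 and 1.0. At an on-study HR of 0.70 the HR runs from 0.703 at delta 1 to 0.999 at delta 10, so a tipping point can be read off.

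For PFS and iPFS, set the 91-day and 13-week analysis limits to the scan interval each subject was permitted, plus window. This reconciles the SAP with the protocol without touching the imaging schedule.

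The cost is SAP wording and one imputation program, with no new data. The small downside is that the delta range must be chosen in advance and shown in full.

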10.2 Sample Size Considerations

10.2.1 Sample Size Considerations for Phase 1b

Six to nine DLT-evaluable subjects will be required to assess the DLT profile of talimogene laherparepvec in combination with pembrolizumab for phase 1b. The sample size of approximately 6 to 9 subjects is determined empirically and is consistent with those used in 6+3 phase 1 designs to evaluate the safety of a single dose of each agent assuming a true incidence rate of DLT is 11 to 33%. Additional subjects, up to a total of 20, will be enrolled in the phase 1b portion of the trial to address the secondary objective exploring the relationship between [REDACTED] and response to treatment.

[figure not shown]

10.2.2 Sample Size Considerations for Phase 3

There are 2 primary endpoints for phase 3, PFS and OS. A 1/3 reduction in hazard ratio (talimogene laherparepvec with pembrolizumab / placebo with pembrolizumab) for PFS (HR = 0.67), and a hazard ratio of 0.70 for OS are hypothesized in the Full Analysis Set. Assuming events follow piece-wise exponential distributions (Figure 1 and Figure 2), the hypothesized HRs will translate into a relative increase of 167% in median PFS time and 44% in median OS time. The absolute increase in median PFS will be 9.4 months (5.6 to 15.0 months) in the talimogene laherparepvec and placebo arm and 12.4 months (28 to 40.4 months) in median OS.

[figure not shown]
Approved

Figure 1. Progression-free Survival

Median PFS (pembrolizumab), 5.6 months; $p(t)$ = event rate at month t ; $p(1.5) = 0.95$; $p(3) = 0.6$; $p(6) = 0.49$; $p(12) = 0.39$; $p(18) = 0.32$; $p(24) = 0.30$; constant hazard in each interval between 2 consecutive pieces; a constant hazard ratio across all pieces.

Figure 2. Overall Survival

Median OS (pembrolizumab) = 28 months; $p(t)$ = event rate at month t ; $p(48) = 0.31$ and $p(60) = 0.27$; constant hazard in each interval between 2 consecutive pieces; a constant hazard ratio across all pieces.

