██ time-to-event endpoints will be analyzed as follows. Time to-event endpoints will be summarized descriptively by treatment group using the Kaplan-Meier (K-M) method. Standard errors of estimated treatment differences by time point will be calculated using Greenwood's formula (Kalbfleisch and Prentice, 1980). KM median estimates will be provided for each treatment arm along with KM estimates at appropriate times for each endpoint (eg, month 3, month 6, month 9, month 12, etc for PFS and 1 year, 2 year, 3 year etc. for OS). In addition, the point estimate of the adjusted risk difference (difference in Kaplan-Meier estimates at the time point of interest, treatment arm – control arm) and the corresponding 95% confidence interval will be provided using the inverse variance-weighted method (see code fragment in [Appendix C](#)). Stratified log-rank test statistics and associated p-values will also be used as the primary analysis method to assess the hypothesis of no treatment difference. Hazard ratios will be estimated using stratified Cox proportional hazards (PH) models (see code fragment in [Appendix C](#)).

For stratified analyses, the stratification factors will include randomization stratification factors per IVRS and PD-L1 status at baseline (positive vs not positive). The criteria for PD-L1 status is as follows:

- Any available PD-L1 positive result makes the subject a positive (irrespective of tissue analyzed and irrespective of the timing).
- If there are more than one PD-L1 result, and none of them are positive, then choose the one from a fresh biopsy.

Listings (eg, baseline characteristics, adverse events and exposure) of subjects in the Retreatment Analysis Set will be provided.

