10.5.4 Sensitivity Analyses

[figure not shown]
Sensitivity analyses will be performed for the Phase 3 portion of the study utilizing the Full Analysis Set to assess the robustness of select primary and secondary endpoints as noted below. Primary analysis method for primary efficacy endpoints as well as the secondary efficacy endpoints will be repeated for the Per Protocol Analysis Set to assess the impact of IPDs. All p-values will be descriptive.

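### The Kaplan-Meier curve for time to first subsequent anti-cancer therapy should be a cumulative incidence curve, because death before therapy is a competing event.

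*SAP*

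**What the plan says.** SAP 10.5.4.2 examines the effect of later treatment on OS through several summaries. One sentence plans three of them: "summarizing the incidence by treatment arm of selected anti-cancer therapies with potential OS benefit", the timing among those who received such therapy, and "K-M and treatment HR estimates of time to first use among all subjects". OS is then re-analysed with censoring at the first selected therapy, and again with inverse probability of censoring weights.

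No rule is given for a subject who dies without starting a selected therapy. SAP 10.1 sets the default: time-to-event "endpoints will be summarized descriptively by treatment group using the Kaplan-Meier (K-M) method". A competing-risk method does appear one bullet earlier in 10.5.4.2, but for OS with possibly informative censoring: "Type (2) censoring will be defined as a competing risk event".

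The parallel bullet for PFS and iPFS in SAP 10.5.4.1 asks only for "treatment HR estimates of time to first use among all subjects", with no curve. For all of these sensitivity analyses, SAP 10.5.4 states: "All p-values will be descriptive".

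**The concern.** The event is first use of a selected therapy, and the analysis covers all subjects. Someone who dies untreated can never have the event. Censoring that death in a Kaplan-Meier curve treats the subject as still able to start therapy later. The complement of the curve is then not the proportion treated. It estimates what use would have been if nobody died first.

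The curve will be read to see how much later treatment each arm received, and so whether that treatment explains or dilutes the OS result. Its error grows with deaths before therapy. If the combination lowers mortality, the error would be expected to differ between arms. A report would also carry two figures for use, one crude and one from the curve, that do not agree.

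**Working it through.** **Anchor to the plan's own figure.** The documents give no figure for time to therapy, so the check starts from the OS design in Protocol 10.2.2 (HR 0.70, 2-sided 0.045, 90% power, 346 events, 330 per arm).

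- Schoenfeld events for a fixed design: 4 × (2.005 + 1.282)² / (ln 0.70)² = 340. This is within 2% of 346, and the rest fits the stated group-sequential adjustment.
- Share censored: 1 − 346/660 = 47.6%, against the stated 48%.

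**Inputs from the plan.** "a hazard ratio of 0.70 for OS are hypothesized in the Full Analysis Set", and "Median OS (pembrolizumab) = 28 months" with a value of 0.31 at month 48. I read 0.31 as the proportion alive, which fits the 28-month median.

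- Dead by 48 months, control: 1 − 0.31 = 69%.
- Dead by 48 months, arm 1: 1 − 0.31^0.70 = 1 − 0.4405 = 56%.

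**Assumed, not in the documents.** True use is 45% in both arms by 48 months. A share s of deaths occurs before any selected therapy. Cause-specific hazards are proportional.

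**Feasible range for s.** Subjects who die after therapy cannot outnumber those who received it, so (1 − s) × 0.69 ≤ 0.45 in control, which gives s ≥ 34.8%. At s = 30%, 48.3% would have to die after therapy when only 45% had it. The range used is therefore 35% to 50%.

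**Formula.** Let C1 be true use and C2 = s × proportion dead. Then 1 − KM = 1 − (1 − C1 − C2)^(C1/(C1 + C2)).

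Example, control at s = 40%: C2 = 0.276, and 1 − 0.274^(0.45/0.726) = 55.2%, which is 10.2 points above the true 45%.

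| s | Control 1 − KM | Excess | Arm 1 1 − KM | Excess | Gap between arms |
|---|---|---|---|---|---|
| 35% | 53.5% | 8.5 | 51.5% | 6.5 | 2.0 |
| 40% | 55.2% | 10.2 | 52.7% | 7.7 | 2.5 |
| 50% | 59.2% | 14.2 | 55.4% | 10.4 | 3.8 |

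The single-arm standard error is √(p(1 − p)/330), about 2.7 points. For a difference it is about 2.7 × √2 ≈ 3.9 points. The error in level is therefore roughly 2 to 5 standard errors within an arm, but the gap is at most about 1.

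**Second model.** A constant therapy hazard (assumed median 30 months, the same in both arms) was set against a share s of the protocol's piecewise OS hazard, multiplied by 0.70 in arm 1. At 36 months 1 − KM is 56.5% in both arms.

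| s (share of OS hazard) | True use, control | Excess | True use, arm 1 | Excess |
|---|---|---|---|---|
| 0.25 | 51.4% | 5.1 | 52.9% | 3.6 |
| 0.50 | 47.0% | 9.5 | 49.6% | 6.9 |
| 0.75 | 43.1% | 13.4 | 46.6% | 9.9 |

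The excess was larger in control in all 63 scenarios built on the design OS hazard ratio: 36 with equal therapy hazards and 27 with arm 1's therapy hazard at 0.67 times control.

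**The case against.** Several points on the other side stand.

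- **Use is also reported without this bias.** The same sentence plans incidence by arm, which death before therapy does not inflate. A reader might infer that the trial's account of subsequent therapy is overstated as a whole; the SAP does not support that. Crude incidence does not replace the curve, though, because it gives no time course and takes no account of unequal follow-up.
- **The hazard ratio is sound.** With deaths censored it is a valid cause-specific hazard ratio.
- **Total deaths are not the driver.** A reader might infer that the arm with more deaths is always overstated more. What matters is deaths before therapy. In a constructed case at 60 months, an arm with 79.5% dead but 12.5% dying untreated is overstated by 9.5 points, while one with 62.9% dead and 24.7% dying untreated is overstated by 15.1.
- **The gap between arms depends on what is held equal.** It arises when cumulative use is equal. With equal therapy hazards, 1 − KM is the same in both arms and cumulative incidence differs (47.0% and 49.6% at s = 0.50), because longer survivors have longer to start therapy. Neither curve alone says whether later therapy explains OS. The censored and weighted OS analyses in the same section address that.
- **Censoring of deaths is inferred.** The SAP does not state it. If death counted as an event, the curve would show therapy or death, which is not the outcome named. The sentence needs changing on either reading.
- **SAP 10.5.4.1 plans no curve,** so the estimator problem does not extend to it.

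**Conclusion.** The point holds for the Kaplan-Meier curve in SAP 10.5.4.2. If deaths before therapy are censored, one minus Kaplan-Meier exceeds the proportion treated in each arm, by more where more subjects die untreated. The direction is certain; the size is not, because therapy use and the share of untreated deaths are assumed. Under the 48-month illustration the excess is about 8 to 14 points in control and 6 to 10 in arm 1. The error in level is the main problem. The gap of 2 to 4 points between arms is within about one standard error of a difference and requires equal cumulative use.

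It would be tempting to conclude that the OS result, or its interpretation, is compromised. The documents do not support that: this is a descriptive sensitivity summary, and the primary OS test, alpha, event goals and power do not depend on it. It is a definite but limited estimator error in a supportive output, worth correcting because the correction costs almost nothing.

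**What to change.** In SAP 10.5.4.2, replace the Kaplan-Meier curve with the Aalen-Johansen cumulative incidence of first selected therapy by arm, taking death before therapy as the competing event. Keep the treatment hazard ratio, state that deaths before therapy are censored in it, and label it cause-specific. Leave the crude incidence and the timing summaries as they are. In SAP 10.5.4.1 only the same hazard-ratio label is needed.

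The cost is a sentence of SAP text and a small programming change. Survival and subsequent anti-cancer therapy are already collected in long-term follow-up (SAP 3.1.4.2), and Appendix C.8 already has code that handles a competing event. No new data are required.
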